7.9.1 Procedures for maintaining and breaking the treatment blind

7.9.1.1 Maintenance of study treatment blind

All subject treatment details will be allocated and maintained by the IRT system. Details of the IRT system will be addressed in a separate randomization schedule specification document.

7.9.1.2 Breaking the treatment blind in an emergency situation

In the event of an emergency, it will be possible to determine to which treatment arm and dose the subject has been allocated by contacting the IRT. All sites will be provided with details of how to contact the system for code breaking at the start of the study. The Medical Monitor or equivalent should be consulted prior to unblinding, whenever possible.

The Clinical Project Manager (CPM) will be informed immediately via the IRT when a code is broken, but will remain blinded to specific treatment information. Any unblinding of the IMP, performed by the Investigator must be recorded in the source documents and on the Study Termination eCRF page.

7.10 Randomization and numbering of subjects

An IRT will be used for assigning eligible subjects to a treatment regimen (as applicable) based on a predetermined production randomization and/or packaging schedule provided by the IRT vendor. The IRT will generate individual assignments for subject kits of IMP, as appropriate, according to the visit schedule.

To enroll a subject (Visit 1), the Investigator or designee will contact the IRT and provide brief details about the subject to be enrolled. Each subject will receive a 5-digit number assigned at Screening Visit (Visit 1) that serves as the subject identifier throughout the study. The subject number will be required in all communication between the Investigator or designee and the IRT regarding a particular subject. Subject numbers and kit numbers will be tracked via the IRT.

To randomize a subject (Visit 2), the Investigator or designee will contact the IRT and provide brief details about the subject to be randomized. The IRT will allocate kit numbers to the subject based on the subject number during the course of the study. The randomization number must be incorporated into the eCRF.

8 STUDY PROCEDURES BY VISIT

Details of the study assessments to be performed at specific time points prior to and after IMP administration are provided in [Table 5-1](#), and an outline of all assessments performed is provided in the sections below.

Visit windows are provided below by visit. The site should adjust the time of the visits to maintain the overall timeframe of the study or study periods.

8.1 Baseline Period (4 weeks)

8.1.1 Visit 1 (Week -4)

The following procedures will be performed:

- Obtain written informed consent. For subjects willing to participate in the genotyping substudy, signature and date of the Genetics Informed Consent form. For subjects/caregivers willing to perform the entry and exit personal outcomes interview/survey, signature and date of consent.
- Call IRT to obtain subject number
- Dispense Subject Trial Card

- Collect demographic data, including habits and lifestyle
- Verify Inclusion and Exclusion criteria (laboratory parameters/ECG/echocardiogram/MRI results may not be available at the visit but assessments need to be performed and evaluated before Visit 2)
- Collect general medical and procedure history
- Collect epilepsy history including etiology, diagnosis, surgery, and seizure history
- Brain MRI to be performed before Visit 2 if no brain MRI was performed in the past 10 years and/or no report is available. If a scan was performed within the last 10 years but the clinical condition of the subject was progressive since the last scan, a new scan should be obtained.
- Obtain the report of past video-EEG by the subject and send to UCB or delegate for review before Visit 2
- Collect AED history
- Obtain Baseline C-SSRS data
- Measure vital signs (pulse rate, systolic BP, diastolic BP, and respiratory rate), in supine position after 5 minutes of rest
- Measure body weight and height
- Perform full physical examination (refer to [Section 11.3.4](#) for details)
- Perform full neurological examination (refer to [Section 11.3.5](#) for details)
- Perform 12-lead ECG and have it assessed by central reader before Visit 2
- Perform echocardiogram and have it assessed by central reader before Visit 2
- Collect blood and urine samples for clinical laboratory analyses
- Collect blood sample for concomitant AED assay
- Perform serum pregnancy test (for all female subjects)
- Record concomitant medication (AEDs and non-AEDs) and procedures
- Record AEs since the signature of the informed consent
- Record health-related outcomes and HRU (refer to [Section 9.5](#) for details)
- Dispense diary and provide instructions on proper completion
- Perform entry personal outcomes interview/survey (can be done at Visit 2 instead) if the subject consented to take part in this activity
- Provide appointment to next visit in 4 weeks

8.2 Treatment Period (16 weeks \pm 1 week from Visit 2)

8.2.1 Titration Period (3 weeks \pm 1 week from Visit 2)

8.2.1.1 Visit 2, Baseline (Day 1, 4 to 5 weeks after Visit 1)

The following procedures will be performed:

- Obtain C-SSRS data since the last visit
- Obtain HADS data
- Obtain SSG data
- Obtain QOLIE-31-P data
- Measure vital signs (pulse rate, systolic BP, diastolic BP, and respiratory rate), in supine position after 5 minutes of rest
- Measure body weight
- Perform brief physical examination (refer to [Section 11.3.4](#) for details)
- Perform brief neurological examination (refer to [Section 11.3.5](#) for details)
- Perform Psychiatric and Mental Status assessment
- Obtain 12-lead ECG
- Collect blood and urine samples for clinical laboratory analyses
- Collect blood sample for concomitant AED assay
- Obtain blood samples for DNA (to be performed only in adults – mentally impaired subjects will be excluded – having given specific consent for it, where ethically accepted and authorized by regulatory agencies), RNA, protein, lipids, and metabolites
- Perform urine pregnancy test (female subjects of childbearing potential only)
- Seizure evaluation (count and type) from subject's daily record card
- Record concomitant medication (AEDs and non-AEDs) and procedures
- Record AEs
- Verify Inclusion and Exclusion criteria (including results of laboratory samples, ECG, MRI, echocardiogram results performed since Visit 1). In the event one of these results is not available, the visit may be delayed by 1 week.
- Verify withdrawal criteria
- Randomize subjects using IRT
- Record health-related outcomes and HRU (refer to [Section 9.5](#) for details), with the exception of socio-professional status
- Perform entry personal outcomes interview (if not done at Visit 1) if the subject consented to take part in this activity
- Dispense IMP using IRT

8.2.1.2 Telephone call (Week 1 \pm 3 days)

Subject will be interviewed to check his/her health condition including, seizure experience, concomitant medications and procedures, and AEs.

8.2.1.3 Visit 3 (Week 2 \pm 1 week)

The following procedures will be performed:

- Verification of withdrawal criteria
- Obtain C-SSRS data since the last visit
- Vital signs measurement (pulse rate, systolic BP, diastolic BP, and respiratory rate), in supine position after 5 minutes of rest
- Perform Psychiatric and Mental Status assessment
- Obtain 12-lead ECG
- Obtain blood sample for random PSL levels at any time between IMP intakes and record accurately the time of last IMP intake and time of the sample.
- Perform urine pregnancy test (female subjects of childbearing potential only)
- Seizure evaluation (count and type) from subject's daily record card
- Record concomitant medication (AEDs and non-AEDs) and procedures
- Record AEs
- Record health-related outcomes and HRU (refer to [Section 9.5](#) for details), with the exception of socio-professional status
- Dispense IMP using IRT
- Check IMP accountability

8.2.2 Stabilization Period (1 week \pm 3 days)

8.2.2.1 Telephone call (Week 3)

Subject will be interviewed to check his/her health condition including seizure experience, concomitant medications and procedures, and AEs. Subject should be informed to call the Investigator within 3 days in case of AEs (in order to eventually consider fallback).

8.2.3 Maintenance Period (12 weeks \pm 1 week)

8.2.3.1 Visit 4 (Week 4 \pm 1 week)

The following procedures will be performed:

- Verification of withdrawal criteria
- Obtain C-SSRS data since the last visit
- Obtain HADS data
- Obtain SSG data

- Obtain QOLIE-31-P data
- Measure vital signs (pulse rate, systolic BP blood, diastolic BP, and respiratory rate), in supine position after 5 minutes of rest
- Measure body weight
- Perform brief physical examination (refer to [Section 11.3.4](#) for details)
- Perform brief neurological examination (refer to [Section 11.3.5](#) for details)
- Perform Psychiatric and Mental Status assessment
- Obtain 12-lead ECG
- Collect blood and urine samples for clinical laboratory analyses
- Obtain MITRA blood samples immediately before IMP intake (maximum 15 minutes before IMP intake) and then 3 times after (between 30 minutes and 3 hours after IMP intake) taken at least 30 minutes apart
- Obtain blood samples for RNA, protein, lipids, and metabolites
- Perform urine pregnancy test (female subjects of childbearing potential only)
- Seizure evaluation (count and type) from subject's daily record card
- Record concomitant medication (AEDs and non-AEDs) and procedures
- Record AEs
- Record health-related outcomes and HRU (refer to [Section 9.5](#) for details), with the exception of socio-professional status
- Dispense IMP using IRT
- Check IMP accountability

8.2.3.2 Visit 5 (Week 8 ±1 week) and Visit 6 (Week 12 ±1 week)

The following procedures will be performed:

- Verification of withdrawal criteria
- Obtain C-SSRS data since the last visit
- Measure vital signs (pulse rate, systolic BP blood, diastolic BP, and respiratory rate), in supine position after 5 minutes of rest
- Measure body weight
- Perform Psychiatric and Mental Status assessment
- Obtain 12-lead ECG (only at Visit 5/Week 8)
- Obtain echocardiogram (only at Visit 6/Week 12) for subjects continuing into the OLE
- Collect blood and urine samples for clinical laboratory analyses (only at Visit 6/Week 12)

- Collect blood samples for concomitant AED assay (only at Visit 6/Week 12) including an additional MITRA sample if the AED sample is not within ± 5 minutes of 1 of the scheduled PSL PK samples
- Obtain MITRA blood sample for random PSL levels at any time between IMP intakes and record accurately the time of last IMP intake and time of the sample.
- Perform urine pregnancy test (female subjects of childbearing potential only)
- Seizure evaluation (count and type) from subject's daily record card
- Record concomitant medication (AEDs and non-AEDs) and procedures
- Record AEs
- Record health-related outcomes and HRU (refer to [Section 9.5](#) for details), with the exception of socio-professional status
- Dispense IMP using IRT
- Check IMP accountability
- Perform exit personal outcomes interview/survey (at Visit 6 or can be done at Visit 7) if the subject/caregiver consented to take part in this activity

8.2.3.3 Visit 7 (Week 16 \pm 1 week for End-of-Treatment or earlier for Early Discontinuation Visit)

The following procedures will be performed:

- Verification of withdrawal criteria
- Obtain C-SSRS data since the last visit
- Obtain HADS data
- Obtain SSG data
- Obtain QOLIE-31-P data
- Obtain CIWA-B data (only for subjects tapering)
- Measure vital signs (pulse rate, systolic BP blood, diastolic BP, and respiratory rate), in supine position after 5 minutes of rest
- Measure body weight
- Perform full physical examination (refer to [Section 11.3.4](#) for details)
- Perform full neurological examination (refer to [Section 11.3.5](#) for details)
- Perform Psychiatric and Mental Status assessment
- Obtain 12-lead ECG
- Collect blood and urine samples for clinical laboratory analyses
- Collect blood sample for concomitant AED assay including an additional MITRA sample if the AED sample is not within ± 5 minutes of 1 of the scheduled PSL PK samples

- Obtain MITRA blood samples immediately before IMP intake (maximum 15 minutes before IMP intake) and then 3 times after (between 30 minutes and 3 hours after IMP intake) taken at least 30 minutes apart.
- Obtain blood samples for RNA, protein, lipids, and metabolites
- Perform urine pregnancy test (for female subjects of childbearing potential discontinuing the study only) and serum pregnancy test (for female subjects continuing in the OLE study)
- Seizure evaluation (count and type) from subject's daily record card
- Record concomitant medication (AEDs and non-AEDs) and procedures
- Record AEs
- Record health-related outcomes and HRU (refer to [Section 9.5](#) for details)
- Dispense IMP using IRT
- Check IMP accountability
- Perform exit personal outcomes interview/survey (if not done at Visit 6) if the subject/caregiver consented to take part in this activity

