- ^j The echocardiogram will be conducted at Visit 1. Echocardiograms will be repeated at Visit 6 for subjects continuing the OLE study. Subjects discontinuing will have an echocardiogram 30 days after last IMP intake at the SFU Visit (except if performed at Visit 6). A repeat echocardiogram will be performed for subjects with a new finding, Grade 2 (moderate severity), or Grade 3 (severe severity).
- ^k An echocardiogram will also be performed 6 months after last IMP intake for subjects exposed to >3 weeks to IMP and discontinuing the study (but not for subjects with <3 weeks exposure).
- ^l AED samples will ideally be taken immediately prior to dose of concomitant medication on each occasion. If this is not possible, then the sample may be taken at any time after dose and the timing of sample in relation to dose should be kept the same (± 1 hour) on each occasion for each subject. Therefore, the timing of visits for each subject when AED samples are collected should be scheduled approximately at the same time whenever possible. Assay of parent PSL and metabolites may be included in the AED panel of tests at Visits 6 and 7.
- ^m On Visits 6 and 7, unless the concomitant AED sample is within ± 5 minutes of a scheduled MITRA sample for PSL assay, a separate, additional MITRA sample will be taken at same time as the concomitant AED blood sample.
- ⁿ Subjects are requested to provide blood samples for measurement of PSL and metabolites whenever possible. On Visits 3, 5, and 6, site personnel should obtain blood samples for measurement of random PSL levels at any time between IMP intake and record accurately the time of last IMP intake and the time of sample collection. On Visits 4 and 7, blood samples for measurement of sparse PK profiles will be collected as follows: immediately before IMP intake (maximum 15 minutes before intake) and then 3 times after (between 30 minutes and 3 hours after IMP intake), taken at least 30 minutes apart. All samples may be taken either at home or in the site or partly at home and partly at the site.
- ^o For all female subjects, serum pregnancy test at Visits 1 and 7 (in case the subject enters into the OLE study) and where applicable. Urine pregnancy test will be used at other visits for female subjects of childbearing potential.
- ^p Seizure counts are collected on the subject's daily record card on a daily basis.
- ^q At each visit following an IMP dispensation, IMP should be presented to check for compliance.

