6. Subjects having on average ≥ 4 spontaneous and observable focal-onset seizures per 28 days (based on Investigator assessment of subject report) with at least 1 seizure during each 4-week interval of the 8-week retrospective Baseline Period prior to entry. Additionally, subjects must experience ≥ 4 spontaneous and observable focal-onset seizures per 28 days (based on Investigator assessment of subject report) during the 4-week Baseline Period.
7. Subject has failed to achieve seizure control with ≥ 4 tolerated and appropriately chosen prior AEDs, including past and ongoing treatment, that were individually optimized for adequate dose and duration. Prior discontinued AED treatment would need to be assessed by the Investigator considering the patient medical records and patient and/or caregiver interview. "Prior AED" is defined as all past and ongoing AED treatments with a start date before the Screening Visit (Visit 1).

Concomitant epilepsy treatment

8. Subject is currently treated with an individually optimized and stable dose of at least 1 and up to 3 AEDs for the 8 weeks prior to the Screening Visit (Visit 1) with or without additional concurrent vagus nerve stimulation (VNS) or other neurostimulation treatments. The latter will not be counted as AEDs for the purpose of eligibility.

Laboratory parameter

9. Subject has clinical laboratory test results within the reference ranges of the laboratory or isolated test results that are outside the specified ranges and that are deemed as not clinically significant by the Investigator.

Birth control

10. Female subjects of child bearing potential must have a negative serum pregnancy test at the Screening Visit (Visit 1), which is confirmed to be negative by urine testing prior to the first dose of IMP at Day 1 (Visit 2) and prior to further dispensing at each study visit thereafter. Subjects will be withdrawn from the study as soon as pregnancy is known.

Female subjects will use an efficient form of contraception for the duration of the study for a period of 3 months after their last intake of IMP. Hormonal contraception may be susceptible to an interaction with the IMP, which may reduce the efficacy of the contraception method. The potential for reduced efficacy of any hormonal contraception method requires that a barrier method (preferably male condom) also be used.

Birth control methods considered as an efficient form of contraception:

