7.2.3 Conversion Period

In case the subjects wish to proceed to the OLE study, the treatments and doses will be adjusted gradually in a blinded way to reach the single-entry dose into the OLE study (PSL 400mg/day) as presented in Table 7-4. During the Conversion Period, the dose of IMP must always be administered as bid morning and evening doses, approximately 12 hours apart.

Subjects taking placebo will be converted to active PSL.

Table 7-4: Conversion Period dosing

Dose Arm	Dose per day (morning-evening) during conversion		
	Week:	Week 16	Week 17
PSL 800mg/day	300-300	200-200	200-200
PSL 600mg/day			
PSL 400mg/day	200-200		
PSL 300mg/day			
PSL 200mg/day	100-100	150-150	200-200
PSL 150mg/day			
PSL 100mg/day	50-50	100-100	150-150
PSL 50mg/day			
Placebo			

OLE=open-label extension; PSL=padsevonil

After completion of Week 18, the dose will be 200-200, the entry dose in the OLE study, EP0093.

Note: Dose adjustments steps may vary in length by ± 3 days per week while overall Conversion Period length should not change by more than 1 week.

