11.2 Laboratory measurements

Laboratory assessments will be conducted using standard methods at a central laboratory. The central laboratory will provide the Investigator with dedicated, standardized sampling equipment (labels, needles, tubes), and a study-specific Laboratory Manual, which will explain how to use the equipment and how to ship the samples to the central laboratory. The laboratory parameters measured are presented in [Table 11-2](#).

The total blood volume drawn for clinical laboratory assessments per subject will be a maximum of 31.6mL by sampling, which includes 2mL for hematology, 5mL for blood chemistry, 5mL and 20 μ L for AED and PSL plasma level (including back-up samples for AED assay), 6mL for genetic substudy, 13.5mL for genomic assessments, and 80 μ L for PK measurements.

Table 11–2: Laboratory measurements

Hematology	Chemistry	Urinalysis
Basophils	ALP	Glucose
Eosinophils	ALT	pH
Hematocrit	AST	RBC
Hemoglobin	Bilirubin	Total protein
Lymphocytes	BUN or urea	WBC
MCH	Calcium	Microscopy (WBC, RBC ^a , casts, crystals, bacteria)
MCHC	Chloride	Other
MCV	Creatinine	FSH ^b
Monocytes	Glucose	
Neutrophils	HDL	
Platelet count	LDH	
RBC count	LDL	
WBC count	Magnesium	
	Potassium	
	Sodium	
	Total bilirubin	
	Total cholesterol	

ALP=alkaline phosphatase; ALT=alanine aminotransferase; AST=aspartate aminotransferase; BUN=blood urea nitrogen; HDL=high density lipoprotein; FSH=follicle stimulating hormone; LDH=lactate dehydrogenase; LDL=low density lipoprotein; MCH=mean corpuscular hemoglobin; MCHC=mean corpuscular hemoglobin concentration; MCV=mean corpuscular volume; RBC=red blood cell; WBC=white blood cell

^a Microscopy will be performed only in case of abnormalities.

^b Only applicable to postmenopausal women

Where applicable (ie, for women of childbearing potential), a serum pregnancy test (β -human chorionic gonadotropin levels) will be conducted at Visits 1 and 7 only. Urine pregnancy test will be used at other visits. If pregnancy is suspected at any time during the study, an interim test should be performed.

Women not agreeing to use birth control must be abstinent or be of nonchildbearing potential, defined as being postmenopausal (for at least 2 years before the Screening Visit [Visit 1]), verified by serum follicle stimulating hormone level >40mIU/mL at the Screening Visit (Visit 1), or permanently sterilized (eg, bilateral tubal occlusion, hysterectomy, bilateral salpingectomy), or congenitally sterile.

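### At Visit 7 inclusion criterion 10 calls for a negative urine pregnancy test before IMP is dispensed, but women entering the open-label extension are scheduled for a serum test whose result is not tied to dispensing

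*Protocol*

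**What the plan says.** Protocol section 6.1, criterion 10, applies to women of childbearing potential. After a negative serum test at screening, pregnancy status must be "confirmed to be negative by urine testing prior to the first dose of IMP at Day 1 (Visit 2) and prior to further dispensing". The requirement continues through the study: "and prior to further dispensing at each study visit thereafter".

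Visit 7 is a dispensing visit. Section 8.2.3.3 and Table 5-1 both list IMP dispensing there, and SAP section 7.1 names Visits 2 to 7 as the dispensing visits. At that visit section 8.2.3.3 schedules a "urine pregnancy test (for female subjects of childbearing potential discontinuing the study only) and serum pregnancy test (for female subjects continuing in the OLE study").

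Table 5-1 footnote o, repeated in substance under SAP Table 2-1, reads "For all female subjects, serum pregnancy test at Visits 1 and 7 (in case the subject enters into the OLE study"), with urine testing at other visits for women of childbearing potential.

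Section 11.2 says that the serum test, for women of childbearing potential, "will be conducted at Visits 1 and 7 only. Urine pregnancy test will be used at other visits". It sets no condition about entering the extension. The same section opens with a general statement: "Laboratory assessments will be conducted using standard methods at a central laboratory".

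Section 11.1.4 describes pregnancy as becoming known through a positive urine test. Withdrawal criterion 12 in section 6.3 refers to a positive pregnancy test without naming the type.

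**The concern.** Criterion 10 works as a gate: the named test must be negative before more drug is handed over. At Visit 7 the schedule replaces that test, for women going on to more padsevonil, with a different one, and attaches no gate to it. A site cannot follow criterion 10 and section 8.2.3.3 to the letter for the same woman.

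What is at stake is a pregnancy safeguard. Conversion IMP leads every subject to padsevonil, and for the placebo arm it is the first exposure in this trial: "Subjects taking placebo will be converted to active PSL". If a serum result is pending when IMP is dispensed, the protocol does not tell the site whether to wait.

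**Working it through.** No figure in the plan needs reproducing. The check sets the four testing rules side by side for Visit 7.

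| Text | Woman converting to the extension | Woman not entering the extension | Result needed before dispensing? |
|---|---|---|---|
| Criterion 10 (6.1) | Urine | Urine | Yes |
| 8.2.3.3 | Serum | Urine | Not stated |
| Table 5-1 footnote o | Serum | Serum not called for; no Visit 7 test named expressly | Not stated |
| 11.2 | Serum | Serum | Not stated |

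1. **Converting women.** The three schedule texts agree on serum. Criterion 10 asks for urine. No text says that serum may stand in for it.

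2. **Women not entering the extension.** Section 8.2.3.3 gives urine and section 11.2 gives serum. These women also receive IMP from Visit 7, because the taper runs for 3 weeks (section 7.2.2). Criterion 10 therefore applies to them too. It is met under 8.2.3.3 but not under 11.2 as written.

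3. **Link between result and dispensing.** The protocol provides for late results elsewhere. Section 8.1.1 accepts that laboratory results may not be back at Visit 1 and requires them to be evaluated before Visit 2. Section 8.2.1.1 lets Visit 2 be postponed by 1 week if one is outstanding. Criterion 10 then adds a urine test before the first dose. Visit 7 has neither a hold for a pending result nor a urine test for converting women.

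4. **Spacing of urine tests for a converting woman.** Urine tests are scheduled at Visit 6 (Week 12) and next at Visit 8, after the 3-week conversion (16 + 3 = Week 19). The nominal interval is 19 − 12 = 7 weeks, with the serum test at Week 16 between them. The wording of section 11.1.4, which mentions only a positive urine test, does not cover that serum result. Criterion 12 does.

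5. **How many women the conflict could touch.** The documents give no sex or completion figures for this trial. As an assumption only, suppose 60% to 80% of the 400 randomized convert and 30% to 45% of those are women of childbearing potential:
   - low: 400 × 0.60 × 0.30 = 72
   - high: 400 × 0.80 × 0.45 = 144
   - placebo share under 1:1:1:1:1 allocation: 72/5 ≈ 14 to 144/5 ≈ 29

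   For comparison, 42 of 55 subjects (76%) in EP0069 entered its extension (section 2.3.1). These counts are of women for whom the texts name different tests. They do not count women given IMP untested.

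**The case against.** The strongest reply is that no woman goes untested. Every converting woman has a serum test at Visit 7 and urine tests at Visits 6 and 8. Section 11.2 requires an interim test whenever pregnancy is suspected, contraception is required during the study, and criterion 12 acts on a positive test of either type. Nothing in 8.2.3.3 waives the demand for a negative result before dispensing, so a site could read the serum test as the means of meeting it. All of this stands, and it limits the point to a mismatch of test type and a missing link between result and dispensing.

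A reader might infer more, in four ways that the documents do not support:

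- **That criterion 10 requires an on-site or immediate result.** It says urine testing and nothing about place or speed.
- **That the serum sample goes to the central laboratory and the result comes back after dispensing.** The general sentence opening 11.2 suggests central testing but does not say so for this test. Table 11-2 does not list a pregnancy test, and no turnaround time is given.
- **That footnote o is a further conflicting rule because it covers all female subjects.** Its Visit 7 serum test is conditional on entering the extension, as in 8.2.3.3. Section 11.2 is the schedule text that stands apart.
- **That only women stopping the drug are protected.** They also receive taper IMP from Visit 7.

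The reply does not remove the contradiction. Criterion 10 names urine and allows no exception, and no passage equates the two tests or makes the serum result a condition for dispensing.

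**Conclusion.** The point holds as a minor inconsistency in a safety rule. For converting women, criterion 10 and the Visit 7 schedule name different tests. For women not entering the extension, sections 8.2.3.3 and 11.2 do. The text permits conversion IMP to be dispensed while a serum result is pending, but does not show that this happens. It should not be read as untested dispensing.

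This conclusion rests on the current wording alone and needs none of the assumed rates above. The practical consequence depends on serum turnaround and on the Laboratory Manual and Study Manual, which are not part of these documents. Sample size, type 1 error and the efficacy analyses are unaffected.

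**What to change.** Reconcile criterion 10, section 8.2.3.3, Table 5-1 footnote o and its copy under SAP Table 2-1, and sections 11.1.4 and 11.2. One statement should settle:

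- which pregnancy test result must be available before IMP is dispensed at Visit 7;
- for which women, covering both those converting and those tapering;
- whether a serum result meets criterion 10, and what happens if it is pending;
- whether section 11.1.4 is meant to cover a positive result from either test.

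The sponsor must choose the rule; this review does not say which is right. The cost is wording in a protocol amendment or a letter to sites, with the SAP footnote updated to match. No analysis changes.
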